**Table 1A. Analysis Visit Window for Efficacy Endpoints IGA, EASI, SCORAD, BSA, GISS**

Visit from SOE	Target Day	Analysis Visit Window Based on Study day*
Screening	<1	<1
Baseline	1	1
Week 1	8	[2,11]
Week 2	15	[12, 22]
Week 4	29	[23, 43]
Week 8	57	[44, 71]
Week 12	85	[72, 99]
Week 16	113	[100, 127]
Week 20	141	[128, 155]
Week 24	169	[156, 183]
Week 28	197	>=184

\* Study days are calculated from the day of 1st injection. Study day = (date of assessment – 1st injection date +1) when date of assessment ≥ 1st injection date; otherwise study day = (date of assessment – 1st injection date). If patient never received any dose of study drug, randomization date will be used in place of 1st injection date.

**Table 2: Analysis Visit Window for Efficacy Endpoints CDLQI, IDQOL, DFI, POEM, CMW, CGID, CGIC**

Visit from SOE	Target Day	Analysis Visit Window Based on Study day*
Screening	<1	<1
Baseline	1	1**
Week 2	15	[2, 22]
Week 4	29	[23, 43]
Week 8	57	[44, 71]
Week 12	85	[72, 99]
Week 16	113	[100, 127]
Week 20	141	[128, 155]
Week 24	169	[156, 183]
Week 28	197	>=184

\* Study days are calculated from the day of 1st injection. Study day = (date of assessment – 1st injection date +1) when date of assessment ≥ 1st injection date; otherwise study day = (date of assessment – 1st injection date). If patient never received any dose of study drug, randomization date will be used in place of 1st injection date.

\*\*Not applicable for CGIC.

**Table 3: Analysis Visit Window for PASQ**

Visit from SOE	Target Day	Analysis Visit Window Based on Study day*
Screening	<1	<1
Baseline	1	1**
Week 4	29	[2, 71]
Week 16	113	[72 155]
Week 28	197	>=156

\* Study days are calculated from the day of 1st injection. Study day = (date of assessment – 1st injection date +1) when date of assessment ≥ 1st injection date; otherwise study day = (date of assessment – 1st injection date). If patient never received any dose of study drug, randomization date will be used in place of 1st injection date.

**Table 4: Analysis Visit Window for Safety labs, Vitals, PK and Biomarkers**

Visit from SOE	Target Study Day in Part B a	Vital signs	Physical examination, ECG, Height, Weight	Lab*	PK, ADA	TARC#, Serum Immunoglobulin profiling, antigen-specific IgE
Baseline	1	≤1	≤1	≤1	≤1	≤1
Week 1	8	[2, 11]				
Week 2	15	[12, 22]				
Week 4	29	[23, 43]		[2, 71]	[2, 43]	[2, 71] #
Week 8	57	[44, 71]			[44, 71]	
Week 12	85	[72, 99]			[72, 99]	
Week 16	113	[100, 127]	[2, 155]	[72, 155]	[100, 127]	[72, 155]# [2, 155]
Week 20	141	[128, 155]			[128, 169]	
Week 24	169	[156, 183]				
Week 28	197	>= 184	>= 156	>=156	>= 170	>= 156

\*Hematology and Blood Chemistry only.

#Only for TARC which was collected at baseline, Day 29, Day 113/EOT and Day 197/EOS.

Note that both scheduled and unscheduled measurements will be considered for determining abnormal/PCSV values for laboratory, vital signs or ECGs as well as the baseline values.

**Rules for visit windows of ePRO data collected daily using eDiary:**

For the daily collected ePRO data (e.g. Pruritus worst scratch/itch NRS, skin pain NRS, sleep quality NRS [patient and caregiver], CNSQ), the analysis visit windows will be implemented following the procedure below:

Step 1: Derive the study day,

- If diary date  $\geq$  1st injection date, then diary study day=diary date – 1st injection date +1;
- Otherwise diary study day=diary date – 1st injection date

Step 2: Windows are defined as diary study day -7 to -1 = BL, 1 to 7 = week 1, 8 to 14 = week 2, etc, with 7 days interval between visit windows.

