- 21 The specific assessments that will be performed at the unscheduled visit will depend upon the reason for the unscheduled visit. In the event of suspected SAEs, such as anaphylaxis or hypersensitivity, additional PK and ADA samples may be collected at or near to the event as practically possible.
- 22 Eligibility based on age at time of screening visit.
- 23 Assent collected from patient, if applicable, as per local regulatory (competent authority/ethics) guidelines, based upon the age and level of maturity of the patient.
- 24 The length of the screening period is not fixed but must not exceed 56 days (including TCS standardization). The length of the TCS standardization period is fixed at 14 days.
- 25 Any unused serum samples collected for dupilumab concentrations or ADA measurements may be used for exploratory biomarker research related to AD, inhibition of the IL-4R α pathway with an antibody, treatment response (PD and or predictive), or vaccine response, as well as to investigate unexpected AEs or to identify markers associated with adverse reactions.

²⁶ Pain and sleep will be assessed daily for the 14 days leading up to the baseline visit, the 7 days leading up to the week 1 visit, the 7 days leading up to the week 2 visit, the 7 days leading up to the week 4 visit, the 7 days leading up to the week 16 visit, and 7 days leading up to the week 28 visit. Parents/caregivers will complete a daily e-diary on these days to record skin pain and sleep in patients.

²⁷ ECGs should be conducted prior to collection of blood samples at visits requiring blood draws.

²⁸ Completed only for the subset of patients with ongoing asthma.

²⁹ Completed only for the subset of patients with a medical history of allergic rhinitis. Caregivers will be instructed on using the e-diary to record the CNSQ for 14 days before baseline/day 1 and for the 7 days preceding visits 7, 19, and 22 (weeks 4, 16, and 28).

³⁰ Optional parental informed consent for use of photographs for educational/marketing purposes (selected study sites only).

³¹ An optional tape stripping sub-study may be performed at a subset of study sites. Parents or legal guardians who agree for their child to participate in the tape stripping sub-study will be required to sign a separate sub-study ICF before collection of the samples. Baseline samples should be collected on day 1/baseline (pre-dose). A second sample will be collected at week 16.

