**Table 1: Assignment of “as-treated” arms**

Randomized to	Treatment Received	Treatment Assignment
Dupilumab	All placebo	Placebo
Dupilumab	≥ 1 Dupilumab dose	Dupilumab
Placebo	>=1 Dupilumab dose	Dupilumab

In addition:

- Nonrandomized but treated patients will not be part of the safety population (SAF); however, their safety data will be presented separately.
- Randomized patients for whom it is unclear whether they took the study drug will be included in the safety population as randomized.

For safety summaries, three analysis periods are defined as follows:

- 16-week treatment period is defined as
  - Day 1 to the study completion date of the planned Week 16 visit (or study day 113 starting from the first dose of study drug if the date of the Week 16 treatment visit is unavailable) for those patients who completed the 16-week treatment period
  - Day 1 to the date of early termination visit, for those patients who did not complete the 16-week treatment period

- Follow-up period is defined as the date after the week 16 visit date (or study day 113 starting from the first dose of study drug if the date of Week 16 treatment visit is unavailable) to the date of the end of study visit
- Overall study Period is defined as Day 1 to the date of the end of study (EOS) visit

The SAF will be the basis for the analyses for the treatment period and overall study period; however, for the analyses for the follow-up period, only a subset of the SAF will be included, which is defined as the patients who entered the follow-up period and had at least one visit after the week 16 treatment visit (EOT).

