**Skin Pain NRS**

Skin pain will be assessed by the parent/caregiver at time points during Part B according to [Appendix 3](#). Skin pain will be measured during Part B using a skin pain NRS that was developed and tested for the study-relevant age group. This is an 11-point scale (0 to 10) in which 0 indicates no pain while 10 indicates worst pain possible. The parents/caregivers will be asked to:

“Think about all the areas of your child's skin with eczema. Answer the question below based on what you observe and what your child tells you (if applicable).”

“How would you rate your child's skin pain at its worst in the past 24 hours?”

Clinical sites will check and remind the parent/caregiver to complete the scale according to the time points in [Appendix 3](#). Parents/caregivers will be instructed on using the scale to record their child's skin pain score at the screening visit. Parents/caregivers will complete the rating scale DAILY for the 14 days prior to the baseline visit, for the 7 days prior to the week 2 visit, for the 7 days prior to the week 4 visit, for the 7 days prior to the week 16 visit, and for the 7 days prior to the week 28 visit. Clinical sites will check parent/caregiver data collected using an e-diary for protocol compliance and remind parents/caregivers to complete their e-diary throughout the study. Higher score indicates worse condition.

The baseline Skin Pain NRS score is defined as the prorated average of the Skin Pain scores reported continuously for 7 days right before the baseline visit (i.e. study day -7 to day -1). For post-baseline Skin Pain NRS score, the weekly mean of daily Skin Pain score is calculated as the average of the available reported skin pain score within the week. For example, if there are 3 scores available in a week, the prorated average = (score1 + score2 + score3)/3.

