### **Caregiver-Reported Nasal Symptom Questionnaire (CNSQ):**

The CNSQ will be used to assess the effect of study drug on symptoms of allergic rhinitis. The summed score will include the following 4 symptoms: runny nose, nasal congestion, nasal itching, and sneezing, each rated on a 0 to 3 scale of severity. The questionnaire will be completed only for the subset of patients with a medical history of allergic rhinitis. It is to be completed by the child's parent or caregiver who fluently speaks a language in which the questionnaire is presented (based on availability of translations in participating countries). Total score is the sum of all symptom scores. If there is one symptom score missing, the total score is set to missing. The minimum and maximum possible values of the total CNSQ score are 0 and 12. Higher score indicates worse condition.

Caregivers will be instructed on using the e-diary to record the CNSQ during the screening period (for the 14 days before baseline/day 1) and for the 7 days preceding visits for weeks 4, 16, and 28 as described in [Appendix 3](#).

The baseline CNSQ score is defined as the average of the CNSQ scores reported continuously for 7 days right before the baseline visit (i.e. study day -7 to day -1). The weekly average CNSQ score (post-baseline) will be calculated as the average of the available reported daily CNSQ score within 7 days prior to the visit. For example, if there are 3 scores available in a week, the average = (score1 + score2 + score3)/3.

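### SAP 6.4 places the visit-linked skin pain, sleep and nasal diaries in fixed study-day weeks; this contradicts SAP 4.4.3 for CNSQ and can leave out collected scores when a visit is off target

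*SAP*

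**What the plan says.** **Analysis rule.** SAP 6.4, in its rules for daily e-diary data, counts study days from the first injection and cuts them into weeks: "1 to 7 = week 1, 8 to 14 = week 2, etc, with 7 days interval between visit windows". Besides itch, it names "skin pain NRS, sleep quality NRS [patient and caregiver], CNSQ" as covered.

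**Collection.** The itch NRS is completed daily throughout the study (SAP 4.4.2). The other diaries are intermittent after baseline:

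- Skin pain and sleep: the schedule footnote in Protocol 6.1 (Table 2) asks for entries in the 7 days before Weeks 1, 2 and 4, then "the 7 days leading up to the week 16 visit, and 7 days leading up to the week 28 visit". SAP 4.4.2 likewise has both diaries completed "for the 7 days prior to the week 16 visit". Nothing is collected around Weeks 8 or 12.
- CNSQ: SAP 4.4.3 has it recorded "for the 7 days preceding visits for weeks 4, 16, and 28".

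**Averaging.** For CNSQ, SAP 4.4.3 defines the weekly value as the "average of the available reported daily CNSQ score within 7 days prior to the visit". For skin pain and sleep, SAP 4.4.2 averages whatever scores exist in the week and sets no minimum.

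**Visit timing.** The Week 16 visit is targeted at day 113, with ±3 days allowed (Protocol Table 2). For clinic measures, SAP 6.4 applies no analysis window to scheduled visits.

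**The concern.** Collection is tied to the visit, and analysis is tied to the first injection. The two coincide only when the visit falls exactly on target. Otherwise some pre-visit scores land in the Week 15 or Week 17 block, where no visit value for these diaries is planned, so the Week 16 result does not use them.

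For CNSQ the SAP gives two rules. Two programmers could each follow the document and derive different Week 16 values.

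Change in patient sleep quality and in skin pain are formally tested, at steps 12 and 13 of the hierarchy in SAP 5.6.3. Their Week 16 values should therefore be defined in only one way before database lock.

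**Working it through.** **Inputs**

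- Fixed week k covers study days 7(k−1)+1 to 7k (SAP 6.4).
- The Week 16 target is day 113 (Protocol Table 2). The SAP safety periods use the same day: "study day 113 starting from the first dose of study drug if the date of the Week 16 treatment visit is unavailable".
- The allowed deviation is ±3 days, so an in-window visit falls on days 110 to 116.
- For a visit on day v, the diary days are v−7 to v−1. This assumes that collection follows the actual visit.

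**Reproducing the plan's figures.** For k = 16 the block starts at 7×15+1 = 106 and ends at 7×16 = 112. The day after it is 7×16+1 = 113, the stated target. The fixed weeks therefore match a visit held exactly on time.

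**Scores kept at Week 16.** The overlap of days v−7 to v−1 with days 106 to 112 is max(0, 7 − |v − 113|).

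| Visit day | Days off target | Scores kept of 7 |
|---|---|---|
| 113 | 0 | 7 |
| 112 or 114 | 1 | 6 |
| 111 or 115 | 2 | 5 |
| 110 or 116 | 3 (limit of window) | 4 |
| 109 or 117 | 4 | 3 |
| 108 or 118 | 5 | 2 |
| 107 or 119 | 6 | 1 |
| 106 or earlier, 120 or later | 7 or more | 0 |

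If the seven in-window visit days were equally likely (an assumption), the average kept would be (4+5+6+7+6+5+4)/7 = 37/7 = 5.3.

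**Other visits.** Weeks 1, 2 and 4 (±3 days) also keep at least 4 of 7. Week 28 (target day 197, block 190 to 196, ±4 days) keeps at least 7 − 4 = 3.

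**Precision in the worst in-window case.** The documents give no day-to-day correlation. Assume an equal correlation ρ between days. The variance of an m-day mean is then proportional to ρ + (1−ρ)/m, and the ratio for 4 days against 7 is:

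- ρ = 0.5: 0.625/0.5714 = 1.09
- ρ = 0.9: 0.925/0.9143 = 1.01

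This is about 9% to 1% more variance in the patient's weekly mean.

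**A visit on day 120.** Its EASI and IGA count as Week 16, because scheduled clinic visits are not windowed. Its diary days are 113 to 119, and none lies in 106 to 112. The pain and sleep values are then missing for a reason other than rescue, withdrawn consent, adverse event or lack of efficacy, so SAP 5.6.2 sends them to multiple imputation. The last pain and sleep values before Week 16 are from Week 4.

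**With visit-linked averaging.** All 7 collected days are usable for any v.

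**The case against.** The strongest reply is that the documents never say the diary follows the actual visit. They refer to the Week 16 visit, and its date lies in the future when the 7-day period opens. The fixed blocks are exactly the seven days before each target day: 1–7, 8–14, 22–28 and 106–112. If the e-diary opened on those nominal days, nothing is lost. This stands as a limit on the claim. The plain wording points to the visit, but the trigger is not stated, so the loss is conditional.

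A reader might infer that ordinary early or late visits lose most or all of their scores, or that completed diaries are routinely replaced by imputation. The documents do not support that. Inside the window at least 4 of 7 scores remain, no minimum is set, and SAP 4.4.2 itself illustrates the average with three scores. Protocol inclusion criterion 10 accepts 4 of 7 days for baseline itch. Total loss needs a deviation more than twice the allowed 3 days, and the documents give no frequency for that. The SAP does plan for COVID-19 disruption, so such delays are possible.

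Fixed blocks also have a merit: every patient is measured at the same time since first dose, on the same days as itch. That is a defensible design choice. It does not explain why the same late visit counts as Week 16 for EASI and IGA but not for its own diary, and it does not remove the CNSQ contradiction.

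**Conclusion.** The point holds in a limited form. The conflict between 4.4.3 and 6.4 for CNSQ is certain and depends on no assumption. For skin pain and sleep, the mismatch between collection and analysis days is real if the diary period follows the actual visit. An in-window Week 16 visit then costs at most 3 of 7 scores and yields a slightly noisier mean, not a missing value. Only a visit 7 or more days off target leaves the endpoint to imputation despite a completed diary.

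The rule does not depend on treatment arm, so nothing here implies bias in favour of either group. IGA, EASI and itch are untouched, which covers the primary, co-primary and key secondary endpoints. The measures affected are patient sleep and skin pain, caregiver sleep (outside the hierarchy) and CNSQ (exploratory, and only in patients with a history of allergic rhinitis). The change is worth making before lock because it is cheap and uses data already collected; the trial's main conclusions do not depend on it.

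**What to change.** In SAP 6.4, keep the fixed study-day weeks for the daily worst scratch/itch NRS. For skin pain, sleep quality (child and caregiver) and CNSQ, define each visit's value as the mean of the available scores in the 7 days before the actual scheduled visit. Use the fixed study-day week as fallback when there was no visit or when no score falls in those 7 days. Align the wording of 4.4.3 and 6.4, and state how the e-diary period was triggered. As a drafting guard, limit the post-baseline average to days from the first injection onward, so that a Week 1 visit before day 8 does not draw in baseline scores.

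The cost is a sentence or two in the SAP and a small programming change, with no new data. The downside is that, for off-target visits, these diaries and itch will cover slightly different days. The fallback may hold no data if entries were made only before actual visits; in that case the value is imputed as it is now.

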**6.5. Statistical Technical Issues**

None.

**7. INTERIM ANALYSIS**

No interim analysis is planned.

The primary analysis may be performed when the last patient completes 16 weeks of treatment duration in order to expedite the submission to regulatory agencies. No changes in the conduct of the study will be made based on this primary analysis. The assessment of co-primary and secondary endpoints performed during the analysis will be the final analysis of the co-primary endpoint and secondary endpoints. Hence, there will be no need for alpha adjustment due to the primary analysis.

In order to maintain study integrity (with respect to the post-treatment follow-up visits, safety visits, and analyses) in the event a decision is made to perform the primary analysis, a dissemination plan will be written. This plan will clearly identify the team (including the statistician) that will perform the primary analysis and all related activities, restrict other clinical team members and other sponsor personnel from access to individual patient treatment allocation and site level analysis results, and ensure that the dedicated team will not participate in the data review or data decisions for the following post treatment analyses. However, the dedicated team can participate in the analysis following the final database lock.

**8. SOFTWARE**

All analyses will be done using SAS Version 9.4 or above.

**APPENDIX 1. PROHIBITED AND RESCUE MEDICATIONS**

Low potency steroids (permitted)	Medium potency steroids (permitted as rescue, prohibited otherwise)
Hydrocortisone acetate 1% cream / Hydrocortisone 1% cream (provided to sites by sponsor) Desonide 0.05% cream Alclometasone dipropionate 0.05% cream	Triamcinolone acetonide 0.1% ointment (provided to sites by sponsor) Triamcinolone acetonide 0.1% cream Fluticasone propionate 0.05% cream Fluocinolone acetonide 0.025% ointment
High Potency steroids (permitted as rescue, prohibited otherwise)	Very high potency steroids (prohibited)
Mometasone furoate 0.1% ointment Triamcinolone acetonide 0.5% ointment	Clobetasol propionate 0.05% ointment Betamethasone dipropionate 0.05% ointment

This is a representative list of TCS to be used in the study based on the American Academy of Dermatology classification. Starting on day -14, all patients will be required to initiate treatment with a low potency TCS using a standardized regimen. Based on investigator discretion, low/mild potency TCS may also be used on areas of thin skin (face, neck, intertriginous, and genital areas, areas of skin atrophy, etc.). Hydrocortisone acetate 1% cream / hydrocortisone 1% cream should be used unless there are known side effects to these agents or due to non-availability due to any reason. In those cases, other low potency TCS such as desonide 0.05% cream or alclometasone dipropionate 0.05% cream can be used. The use of medium/high potency steroids should be reserved for rescue. It is recommended that triamcinolone acetonide 0.1% ointment be used for rescue. However, other medium or high potency TCS may be used as per investigator discretion. The use of very high potency steroids is not allowed during the study.

## APPENDIX 2. LIST OF ANALYSIS

### Efficacy Analysis:

Parameter(s)	Analysis Populations	Endpoints	Primary Statistical Method	Supportive/Sensitivity Statistical Method	Subgroup Analysis
Investigator's Global Assessment (IGA) (Primary)	FAS	
 
IGA 0 to 1 (Categorical)
 
	
 
CMH test adjusted by randomization strata (IGA Severity, Region, and Baseline weight)
 
	Tipping point analysis	Yes
Eczema Area and Severity Index (EASI)  (EASI-75 Co-primary, for EU only)	FAS	Categorical: 
 
EASI 75
 
EASI 50
 
EASI 90
 
 Continuous: 
 
% change from baseline
 
	
 
Categorical: CMH test adjusted by randomization strata for categorical variables
 
Continuous: Multiple imputation (MI) using pattern mixture ((MI-WOCF) ) with ANCOVA for continuous variables
 
	Tipping point analysis for co-primary endpoint only.	Yes; For EASI-75 and % Change from baseline
Pruritus worst scratch/itch score (NRS)	FAS	Categorical: 
 
NRS score <math>\geq 3</math>
 
NRS score <math>\geq 4</math>
 
 Continuous: 
 
% change from baseline
 
Change from baseline
 
	
 
Categorical: CMH test adjusted by randomization strata for categorical variables
 
Continuous: Multiple imputation (MI) using pattern mixture (MI-WOCF) with ANCOVA for continuous variables
 
	No	Yes for % change

Parameter(s)	Analysis Populations	Endpoints	Primary Statistical Method	Supportive/Sensitivity Statistical Method	Subgroup Analysis
Skin Pain NRS	FAS	
 
Change from baseline
 
	Multiple imputation (MI) using pattern mixture (MI-WOCF) with ANCOVA for continuous variables	No	No
Sleep quality NRS	FAS	
 
Change from baseline [Patient, Caregiver]
 
	Multiple imputation (MI) using pattern mixture (MI-WOCF) with ANCOVA for continuous variables	No	No
Body Surface Area (BSA) Involvement of Atopic Dermatitis	FAS	
 
Change from baseline
 
	Multiple imputation (MI) using pattern mixture (MI-WOCF) with ANCOVA	No	No
SCORing Atopic Dermatitis (SCORAD)	FAS	
Continuous:
 
 
% change from baseline
 
 
Categorical:
 
 
SCORAD50
 
SCORAD75
 
SCORAD90
 
	
 
Multiple imputation (MI) using pattern mixture (MI-WOCF) with ANCOVA for continuous variables
 
CMH test adjusted by randomization strata for categorical variables
 
	No	No
Dermatitis Family Index (DFI)	FAS	
 
Change from baseline
 
	Multiple imputation (MI) using pattern mixture (MI-WOCF) with ANCOVA	No	No
Global Individual Signs Score (GISS)	FAS	
 
Change from baseline
 
	Multiple imputation (MI) using pattern mixture (MI-WOCF) with ANCOVA for continuous variables	No	No
Patient Oriented Eczema Measure (POEM)	FAS	
 
Change from baseline
 
	
 
Multiple imputation (MI) using pattern mixture (MI-WOCF) with ANCOVA for continuous variables
 
	No	No

Parameter(s)	Analysis Populations	Endpoints	Primary Statistical Method	Supportive/Sensitivity Statistical Method	Subgroup Analysis
Children Dermatology Life Quality Index (CDLQI) ( $\geq 4$ years of age)	FAS	
 
Change from baseline
 
	
 
Multiple imputation (MI) using pattern mixture (MI-WOCF) with ANCOVA for continuous variables
 
	No	No
Infants' Dermatology Quality of Life Index (IDQOL) ( $< 4$ years of age)	FAS	
 
Change from baseline
 
	
 
Multiple imputation (MI) using pattern mixture (MI-WOCF) with ANCOVA for continuous variables
 
	No	No
TCS	FAS	
 
Proportion of TCS medication-free days from baseline to week 16
 
Mean weekly dose of TCS in grams for low potency TCS from baseline to week 16
 
	
 
CMH test adjusted randomization strata
 
ANCOVA for continuous variables
 
	No	No
Caregiver missed workdays (CMW)	FAS	
 
Mean of caregiver missed workdays
 
	
 
Descriptive statistics by visit/time
 
	No	No
Caregiver global impression of disease (CGID)	FAS	
 
Proportion of patients with No symptoms at week 16
 
proportion of patients with No symptoms or Mild at week 16
 
	CMH test adjusted randomization strata	No	No
Caregiver global impression of change (CGIC)	FAS	
 
Proportion of patients with ratings = "Much better" at week 16
 
Proportion of patients with ratings = "Much better" or "Moderately better" at week 16
 
	CMH test adjusted randomization strata	No	No

Parameter(s)	Analysis Populations	Endpoints	Primary Statistical Method	Supportive/Sensitivity Statistical Method	Subgroup Analysis
PASQ (for patients with Asthma)	FAS	
 
PASQ total score based on questions 3-6
 
	Multiple imputation (MI using pattern mixture (MI-WOCF) with ANCOVA for continuous variables	No	No
CNSQ (for patients with medical history of allergic rhinitis)	FAS	
 
Change from baseline in CNSQ score at week16
 
	Multiple imputation (MI using pattern mixture (MI-WOCF) with ANCOVA for continuous variables	No	No
IGA	FAS	
 
Proportion of patients who achieve reduction of IGA score by <math>\geq 2</math> from baseline to week 16
 
	CMH test adjusted randomization strata	No	No
IGA and EASI	FAS	
 
Proportion of patients with IGA score 0 or 1 or EASI-90 at week 16
 
	CMH test adjusted randomization strata	No	No

